For women who are nonadherent to CRC screening guidelines but adherent to BC screening (Group A), the TIWeb and the CSC will encourage CRC screening by building on the women's success with regular BC screening. For women who are nonadherent to both CRC and BC screening (**Group B**), the TIWeb and the CSC interventions will promote both CRC and BC screening simultaneously. Research indicates that individuals who undergo one type of cancer screening are more likely to pursue other forms of screening,⁽¹³⁾ making a holistic approach to cancer screening efficient and consistent with what would happen in a routine preventive care visit. In the proposed study, we also will test the cost-effectiveness of each intervention arm and the intervention interactions with demographic and practice variables. Past research^(14, 15) has shown that interventions vary in both cost and efficacy, making the addition of cost-effectiveness analysis important for future translation to practice. We will use a 2X2 factorial design with women randomly assigned to receive one of the following: 1) usual care, 2) a TIWeb, 3) a Cancer Screening Call (CSC), or 4) a TIWeb plus a CSC.

Aim 1: Compare the efficacy (adherence and stage) of four conditions to promote CRC and BC screening among women ages 50 to 75: 1) usual care; 2) a mailed TIDVD; 3) a CSC, and 4) a mailed TIDVD + a CSC. All women will be non adherent to CRC screening and may or may not be adherent to BC screening. 50 **Group A (nonadherent to CRC screening guidelines but adherent to BC screening guidelines)**

Hypothesis 1 (Primary outcome): There will be differences in CRC screening adherence and stage of adoption, when controlling for adherence to BC screening at baseline, among women who are randomized to 1) usual care; 2) a TIWeb; 3) a CSC, and 4) a TIWeb plus a CSC.

Group B (nonadherent to both CRC and BC screening guidelines)

Hypothesis 2 (Secondary outcome): In the group that is nonadherent to both CRC and BC screening at baseline, there will be differences in adherence to both CRC and BC screening and stage of adoption, among women who are randomized to 1) usual care; 2) a TIWeb; 3) a CSC, and 4) a TIWeb plus a CSC.

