Women for the CAB will be selected in the same way as those who participate in the larger study but will be ineligible for the larger study. Selected participants will be representative of women in the target populations with regard to age and race.⁽¹³⁰⁾ Other qualitative methodologists^(131, 132) indicate that three to five sessions are sufficient to achieve redundancy or "saturation" of information. The program's usability will be evaluated by assessing ease of use, content (leveling and appropriateness), aesthetic appeal, and cultural relevance. The program will also branch women dependent on whether answers to risk factors identify them as average or high risk for CRC due to family history. Women at average risk will be offered options of FOBT or colonoscopy. For women at increased CRC risk due to family history, colonoscopy will be recommended as the most appropriate test. If a woman at increased risk is not interested in colonoscopy, FOBT will be offered. The interactive programming allows users to receive feedback after each question or short series of questions. For individuals in **Group A (Figure 3)**, the program will provide messages to increase CRC screening that build on the success with BC screening using the common principles identified in the theoretical framework. The program will begin with risk messages that include age and stage of adherence. For women who are non-adherent to both cancer screenings (**Group B**), the program will branch to messages designed to promote both CRC and BC screening behaviors simultaneously. (**Figure 4**) For both groups of women, benefits and barriers to screening will be individually tailored. For barriers, each individual item will be listed so that all perceived barriers can be included. For women who have never had previous CRC or BC screenings or for those whose answers indicate low self-efficacy, the TIWeb will include a video of the procedures. Women receiving TIWeb will be able to observe video demonstrations of mammography and CRC screening tests as appropriate, and to listen to testimonials from health providers and survivors. Animated graphics and charts will be included. *For example, for women in Group A, message tailoring will target CRC screening because they are already adherent to BC screening. However, the message will incorporate illustrations that relate back to their adherence to BC screening.*

Table 3. Differences in Benefits Messages between Women in Group A and Group B

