Messages: The tailoring for each construct occurs when a woman's answer to a key question prompts delivery of the appropriate message. For **Group B**, several scenarios might present depending on a woman's staging answers for BC and CRC screening. **Table 2** illustrates how messaging could be combined depending on these categories. Additionally, depending on answers to

prototypes will be finalized. We estimate that approximately 800 unique photographs will be acquired through on-site photography/ videography and digital imaging libraries. Full-motion video clips (500) will be used to show mammography and CRC screening procedures and to present key testimonials and other material as media space allows. Illustrations will be multimedia firm and, if appropriate, obtained from stock illustration libraries. Graphics will be integrated within the interface to ensure consistency of themes(s) and user experience. A visual animation will demonstrate how cancer that is not detected early can grow and spread through the body. Animation will also be used within charts or graphs to emphasize important elements, and animated icons and sound designed by the will be incorporated throughout the program to enhance the look, feel, consistency, and usability of the program. All pages will have spoken (audio) dialogue with the same information repeated in the form of written text, allowing women with low literacy to use the program. Our goal is to create a tailored

Table 5. CSC Intervention Objectives, Constructs and Content

Construct	Objective	Telephone Counseling Content	Time Mins
Intro	Establish rapport	
 • Identification of Counselor as nurse • Verify participant identification • Review purpose of call • Identify adherence and stage with BC and CRC 	1
Objective risk	Identify objective risk	
 • Assess family hx • Information about individual risk 	3
Knowledge	Increase knowledge of CRC & BC screening options depending on individual risk and choice	
 • Assess knowledge of options • Clarify misconceptions • Answer questions • Provide options of FOBT or colonoscopy and mammography for Average Risk individuals and colonoscopy and mammography information for High Risk individuals 	5
Benefits	Increase benefits of CRC & BC screening	
 • Information about benefits • Clarifying misconceptions • Answer questions 	2

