D.12. Sample Size and Power Analysis: The *primary efficacy hypothesis in this area of research is adherence to screening. Therefore, adherence to CRC and BC screening at 6 months has driven our choice of sample size.* Originally, we proposed conducting analysis with two separate groups based on initial mammography status: 1) women who were adherent to mammography but not to colorectal cancer (CRC) screening, and 2) women who were adherent to neither mammography nor CRC screening. By testing these groups separately, we required a sample size of 2616 to achieve 80% power between both the control and intervention groups and between any combinations of groups. In re-considering this approach, we realized that since the outcome of CRC screening was common across both groups A and B, this was not the most efficient design to test our outcomes. We are proposing analyses using one group of women, all of whom will be non-adherent to CRC screening at baseline. In this group, some women will be adherent to mammography guidelines (i.e., had a mammogram in the past 15 months) and others will be non adherent. For Aim 1, when we examine intervention effects on the outcome of CRC screening, we will control for baseline adherence to mammography. For Aim 2, we will use only the sub-group of women who were not adherent to either breast or CRC screening at baseline. Using this approach will reduce the sample size needed and reduce the overall costs of the study, more closely aligning the budget with the amount awarded. Most importantly, revising our analytical approach will enable us to achieve our initial Aims despite the reduced sample size.

Specifically, for the outcome of CRC screening adherence, we had justified sample size in the original proposal to achieve 80% power to detect differences between intervention groups, *separately* for two groups of women depending on their baseline breast cancer screening adherence status.

Group A includes women who were nonadherent to CRC screening but adherent to BC screening, and **Group B** includes women nonadherent to both CRC and BC screening.

We realize now that it is unnecessary to perform the analysis of CRC adherence separately for the two groups (A and B). Instead the Group variable (A vs B) can be entered in the model using baseline mammography screening as a covariate.

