Thus, the hypotheses for Aim 1 can now be conceptualized as

Aim 1:

Hypothesis 1 (Primary outcome): There will be differences in CRC screening adherence and stage of adoption, when controlling for adherence to BC screening at baseline, among women who are randomized to 1) usual care; 2) a TIDVD; 3) a CSC, and 4) a TIDVD plus a CSC.

Aim 2:

Hypothesis 2 (Secondary outcome): In the group that is nonadherent to both CRC and BC screening at baseline, there will be differences in adherence to both CRC and BC screening and stage of adoption, among women who are randomized to 1) usual care; 2) a TIDVD; 3) a CSC, and 4) a TIDVD plus a CSC.

D.13. Analyses. Descriptive statistics will be computed for all variables, using stem-and-leaf plots, central tendency indices, variability indices, and frequency distributions. We will compare demographic information at baseline across the four randomized groups (usual care, TIWeb, CSC, and TIWeb + CSC), using the analysis of variance (ANOVA) for continuous variables (describing with means and standard deviations) and using the Pearson chi-square test for categorical variables (describing with cross-classification tables). If the ANOVA parametric assumptions of normality and equal variances are not met, we will perform the nonparametric Kruskal-Wallis test for the continuous variables. If there are significant baseline differences between the two intervention groups at a liberal significance level of 0.20, we will adjust for those characteristics in subsequent logistic regression analyses.

Aim 1: Analysis for intervention efficacy: Women in **Group A women** are nonadherent to CRC screening but adherent to BC screening at baseline and thus could become adherent to *CRC screening*. *Depending on whether a woman is at increased risk (due to family history) or average risk, we will code each participant as risk-appropriate adherence or adherence to any CRC screening. For women at average risk, these categories will be identical. For women at high risk, completion of a colonoscopy is needed to classify them as adherent to the risk-appropriate test. Thus, two outcomes will be tested in relation to CRC adherence: 1) adherence to any CRC test; and 2) adherence to a risk-appropriate test. Women in Group B will be nonadherent to both CRC and BC screening at baseline and thus could remain nonadherent to both, become adherent to one, or become adherent to both screenings.*

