
logistic regression models will be tested using the likelihood ratio test.⁽¹⁴¹⁾ Adjusted odds ratios and profile-likelihood-estimated 95% confidence intervals for those odds ratios will be provided.

Analyses of stage of screening will be the same as analyses above for adherence, except that the binary outcome is advancement (from baseline) in stage of adoption for CRC screening guidelines. There are two possible stages of adoption at baseline (precontemplation and contemplation) and three possible stages at 6 months (precontemplation, contemplation, and action). Thus, there are four possible stage movements from baseline to 6 months (fall back one stage, remain the same, advance one stage, or advance two stages). However, data on a large sample in the Preliminary Studies demonstrated that, of 904 women followed to 9 months post-baseline, only 4% of women fell back one stage and only 6% advanced two stages; the majority either advanced one stage (50%) or remained the same (39%). Therefore, we will implement the outcome of stage change as a dichotomous variable: improvement (advance one or two stages) versus no improvement (remain the same or fall back one stage).

Group B (nonadherent to both CRC and BC screening guidelines)

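### Aim 1 does not fix one primary variable: two codings of CRC adherence are left unranked, and stage of adoption shares the primary label although D.12 sizes the trial on adherence alone

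*Combined protocol and SAP*

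**What the plan says.** Three places bear on what is primary for Aim 1.

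- **Hypothesis 1** (A. Specific Aims, repeated at the end of D.12): "Hypothesis 1 (Primary outcome): There will be differences in CRC screening adherence and stage of adoption". Adherence and stage stand under one label.
- **D.12, Sample Size and Power Analysis**: "primary efficacy hypothesis in this area of research is adherence to screening". The heading of the revised power table likewise names CRC adherence as the Aim 1 primary outcome. Stage has no planning rate and no power.
- **D.13, Aim 1**: "Thus, two outcomes will be tested in relation to CRC adherence: 1) adherence to any CRC test; and 2) adherence to a risk-appropriate test". The section adds: "For women at average risk, these categories will be identical". The two codings therefore differ only in women with a family history of CRC. On stage, D.13 says: "Analyses of stage of screening will be the same as analyses above for adherence".

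D.11 sets the primary time point at 6 months but lists mammography alongside CRC tests as primary. The multiple-comparison paragraph of D.13 covers Exploratory Aim 3 only. No significance level is stated for Aim 1.

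**The concern.** A primary variable should be identifiable before outcomes are seen. Here D.12 and Hypothesis 1 disagree on whether stage is primary. Even if D.12 governs, CRC adherence still means two variables, both to be tested. An analyst could report whichever of up to three tests reaches significance as the primary result, without breaking any written rule. That raises the error rate within every single arm comparison, before the number of arm pairs is considered. It also leaves unclear which coding the power table supports.

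**Working it through.** **1. Reproduce the plan's power.** Inputs from the D.12 table: 20/30/40/55% and 357 per arm at 6 months. Two-sided 0.05 is assumed. With pooled variance and no continuity correction:

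power = Φ{[|p1 − p2| − 1.96·√(2p̄(1−p̄)/n)] / √[(p1(1−p1) + p2(1−p2))/n]}

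For website v call (30% v 40%), p̄ = 0.35:

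- null SE = √(0.455/357) = 0.0357, and 1.96 × 0.0357 = 0.0700
- alternative SE = √(0.45/357) = 0.0355
- power = Φ(0.0300/0.0355) = Φ(0.846) = 0.80, as stated

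The other pairs also agree: usual care v website 0.871 (stated .87), call v combination 0.981 (stated .98), and the remaining three above 0.999 (stated .99). The required n for 30% v 40% is 356, and 357/0.9 = 397. The sizing therefore spends the whole 0.05 on one outcome and one pair.

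**2. Null error for one pair.** The documents do not give the higher-risk share, the test mix or the movement in stage. The assumptions are:

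- 357 per arm and adherence A of 20 to 30% in both arms
- higher-risk share f of 10 to 20%, with half of those women's tests being colonoscopy
- share of precontemplators c of 40 to 60%
- 40% of unscreened precontemplators moving to intention

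The outcomes are nested: risk-appropriate adherence lies within any-test adherence, which lies within stage advance (taking the Table 6 Action row that accepts any test). The cell probabilities are:

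- risk-appropriate test: A(1 − 0.5f)
- other CRC test: 0.5Af
- stage advance without a test: 0.4c(1 − A)
- none: the remainder

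For example, A = 0.30, f = 0.20 and c = 0.60 give 0.27, 0.03, 0.168 and 0.532. Simulating two equal arms with two-sided z-tests gives:

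| Tests that may be claimed | P(at least one p<0.05) |
|---|---|
| one named coding | 5% (nominal) |
| either adherence coding | 6.1–6.9% |
| either coding or stage | 9.0–10.2% |

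Independent tests would give 1 − 0.95² = 9.8% for two and 1 − 0.95³ = 14.3% for three. The overlap between outcomes keeps the figures below those.

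A wider set of assumptions gives 5.7–7.4% for the two codings and 9.5–11.5% with stage, using the four-arm chi-square test. Those assumptions are 20% adherence, 5–30% higher risk, 30–70% of higher-risk women's tests not colonoscopy, and stage advance of 40–56%.

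**3. What keeping several primaries would cost.** Using n = [z(1−α/2)·√(2p̄(1−p̄)) + 0.8416·√(p1(1−p1) + p2(1−p2))]² / (p1 − p2)² for 30% v 40%:

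| Primaries (Bonferroni α) | Power at 357 | Evaluable n per arm | Enrolled per arm (n/0.9) |
|---|---|---|---|
| 1 (0.05) | 0.80 | 356 | 397 (from the plan's 357) |
| 2 (0.025) | 0.71 | 432 | 480 |
| 3 (0.0167) | 0.66 | 475 | 528 |

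These use the adherence rates, because the plan gives none for stage or for a separate risk-appropriate coding.

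**The case against.** The best defence is that D.12 already settles the hierarchy. It calls adherence the primary efficacy hypothesis and powers CRC adherence alone, and D.11 sets 6 months. Stage then looks like loose wording in Hypothesis 1. The two adherence codings are also almost one variable, so choosing between them gains little. Much of this stands: a reader might infer three equal co-primaries, and D.12 does not support that. Most of the inflation comes from stage. What remains is that the hypothesis label contradicts D.12, and neither D.11 nor D.12 says which coding is meant.

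Two stronger inferences should be resisted.

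**That the two codings would rank website and call differently.** For a higher-risk woman the website section (D.6.2) says "If a woman at increased risk is not interested in colonoscopy, FOBT will be offered", while Table 5 lists for the call "colonoscopy and mammography information for High Risk individuals". But the call arm also provides FOBT: D.1 offers it, the Table 5 access row mails it, D.7 has counselors offer the cards, and D.8 builds a risk algorithm into both interventions and mails kits on request. D.11 expects some higher-risk women to choose FOBT and does not distinguish by arm.

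If a share q of higher-risk women's tests is not colonoscopy, a true reversal at the planned 30% v 40% needs f > (0.40 − 0.30)/(0.40·q_call − 0.30·q_web). That is 0.10/0.40 = 25% even at q_call = 1 and q_web = 0, and 0.10/(0.32 − 0.06) = 38.5% at 0.8 and 0.2. With arms only 1 to 2 points apart, about 3 to 12% would suffice. But 2 points against an SE near √(2 × 0.4 × 0.6/357) = 0.037 is z of about 0.5, so no ranking could be claimed.

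**That Table 6 lets any test count as Action for women staged by colonoscopy intention.** One Action row does. A second row requires colonoscopy for these women. Only the choice of row is open.

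**Conclusion.** The concern holds in a limited form. Hypothesis 1 and D.12 conflict on whether stage is primary, the two CRC adherence codings are unranked, the planned rates are tied to neither, and no multiplicity rule covers Aim 1. The nominal 5% for a single comparison becomes about 6 to 7% through the choice of coding, and 9 to 10% only if stage is also claimed as primary. Both ranges rest on assumed inputs for higher-risk share, test mix and stage movement. The sample size calculation is correct for one primary outcome and would be too small for two or three adjusted ones.

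**What to change.** In Hypothesis 1, D.11 and D.13, name one primary variable: adherence to any CRC test at 6 months. This coding is consistent with the D.2 entry definition, which accepts any of the listed tests. It is a choice of endpoint and implies nothing about which test a woman should have. State in D.12 that 20/30/40/55% refer to this coding. Label risk-appropriate adherence and stage advance as secondary, and say which Table 6 Action row the stage outcome uses. Bring the D.11 sentence that lists mammography as primary into line with Hypothesis 2, where BC screening is part of a secondary outcome.

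A fixed testing sequence is not needed; the secondary label is enough and leaves stage open to analysis if adherence shows no difference. The cost is wording only, settled before outcomes are examined, and 397 per arm stands. The downside is that risk-appropriate adherence and stage lose primary status.

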D.1. Research Design. We propose a prospective randomized 2X2 factorial design: 1) usual care; 2) aTIWeb; 3) a Cancer Screening Call (CSC), and 4) a TIWeb + a Cancer Screening Call (CSC). The intervention will be tested in two groups of women. **Group A** will include women who are nonadherent to CRC but adherent to BC screening guidelines. **Group B** will include women who are nonadherent to both CRC and BC screening guidelines. Random assignment to intervention

arms will be performed within both **Group A and Group B**. A periodic list of eligible women will be pulled from databases and sent to the research study office at IUSON. The list will then be forwarded to the co-investigator in charge of recruitment ([name], Executive Director for the Indiana Family Practice Research Network) and the physicians for the opportunity to review their own patient list. This information will consist of name, DOB/age, address, and phone number. An additional field will include mammogram status, indicating whether the individual has a documented mammogram in the past 15 months. Then a letter, brochure, and refusal postcard will be sent to potentially eligible women. A parsed list of women who don't opt out by returning the refusal post card, calling a toll free number, or emailing the project manager (number and email provided on brochure) will be scheduled for a recruitment phone call. Participants in the TIWeb Intervention Arm will be given access to a TIWeb that is programmed to provide an intervention that is interactive and tailored to the participant's individual beliefs and demographics. Individuals receiving the TIWeb will be given information that allows them to call and receive an FOBT kit in the mail or schedule an appropriate CRC test and/or mammogram. The physicians at the recruitment sites will have reviewed the list of potential participants before recruitment to ensure they are candidates for screening tests.

Figure 2. Study Schema

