In Table 8 of the original application (see appendix), we proposed enrolling 327 for each of 8 combinations of 4 arms and 2 groups (A and B) for a study total of 2616. However, using this alternative approach will require only 1308 (327 in each of the 4 arms) women to test the primary outcome of CRC adherence. However, new studies, including our own, indicate 15-20% adherence to CRC screening in control conditions. Our initial proposal anticipated on 10% adherence in the control arm. Thus, although the new design decreases the sample size by combining the groups, a more realistic estimate of the adherence in the control group will actually increase the sample size compared to our estimate in Group A for the initial proposal. Specifically, we propose to increase our estimate of CRC adherence in all four arms, to accommodate a change in the proposed adherence in the control group from 10% to 20%. This will require 397 instead of 327 per arm (see Table 1). Thus, a sample of 397 per group at baseline (357 per group at 6 months after 10% estimated attrition) will provide 80% power to detect differences between any pair of the four randomized arms for Aim 1 (Table 1).

Revised Sample size and Power analysis for primary efficacy hypothesis of estimated CRC screening adherence rates in the combined groups of those adherent (Group A) and non-adherent (Group B) at baseline to breast cancer screening (Aim 1, primary outcome of CRC adherence)

GROUPS A and B combined

Time	Usual Care (1)	TIDVD (2)	CSC (3)	TIDVD+CSC (4)	Power
Baseline adherence	0%	0%	0%	0%	NA
Total sample size (N):	(n = 397)	(n = 397)	(n = 397)	(n = 397)	
N by baseline strata, Adherent to BC (A) Non-adherent to BC (B)	(n = 119) (n = 278)				
6 months adherence	20%	30%	40%	55%	Power for 357/arm (Groups A and B combined)
Total sample size (N):	(n = 357)	(n = 357)	(n = 357)	(n = 357)	1v2 .87 1v3 .99 1v4 .99 2v3 .80 2v4 .99 3v4 .98
N by baseline strata, Adherent to BC (A) Non-adherent to BC (B)	(n = 107) (n = 250)				

Enrollment will be stratified by women adherent to breast but not CRC screening and those adherent to neither in a 30%/70% ratio so that we will have an adequate sample to detect an 80% power for Aim 2. Aim 2 will use only the subgroup of women who are not adherent to either breast or CRC screening. This will provide at least 80% power for Group B for comparing each pair of randomized arms, when testing the secondary outcome (adherence to both CRC and BC screening) (Table 2).

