Group A (nonadherent to CRC but adherent to BC screening guidelines)

Hypothesis 1- Efficacy Analysis: The differences in binary adherence across the four randomized arms will be tested initially with the chi-square test for a 2x4 cross-classification table (adherence by randomized intervention groups). Binary logistic regression analysis, with three dummy variables using usual care as the reference category, will be computed to study the effects of each intervention (TIWeb, CSC, TIWeb +CSC) versus usual care on adherence, while adjusting for any potentially confounding covariates. In addition, model contrasts will be specified to statistically compare each of the three intervention arms to the others. Since the intervention is delivered to the patient and not the provider, analysis of variation in CRC screening by practitioners will be limited. Outcomes of patients who share the same providers may be slightly more correlated than outcomes of patients from different providers. Thus, the within-provider correlation among patients will be assessed with variance components, and if necessary generalized estimating equations (GEE) will be used with logistic regression to account for the within-provider correlation. We will enter as independent variables into logistic models the following: randomized group membership and any demographic covariate (age, race, education, marital status, screening history, baseline stage of adoption, SF12 mental health component, SF12 physical health component) for which the randomized groups differ significantly at baseline using a liberal significance level of 0.20. We will also measure whether subjects report that their physicians have recommended the screening test in the past and the amount of out-of-pocket expense for screening and enter these as covariates. In addition to demographic variables, other potential covariates will be location of TIWeb intervention (use of a computer at home or elsewhere), and whether women in the TIWeb group needed technical help from the research assistant to use the TIWeb program. We plan to include screening history as a covariate in our analysis by using the total number of past screenings for each test since the participant turned 50. For analysis with mammography screening, one covariate will be included (total number of mammograms since age 50). For the analysis of CRC screening, two covariates will be included simultaneously in the models (total number of FOBTs since age 50, and "any previous endoscopic test" [yes/no]). The CRC screening analysis requires two covariates because a history of five FOBTs, for example, is not equivalent to one previous FOBT and one previous colonoscopy or sigmoidoscopy. All variables in the

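### D.13 still confines the primary CRC-adherence analysis to Group A (about 107 women per arm), although D.12 plans and powers it in Groups A and B combined (357 per arm)

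*Combined protocol and SAP*

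**What the plan says.** D.12 (Sample Size and Power Analysis) explains the redesign: "We realize now that it is unnecessary to perform the analysis of CRC adherence separately for the two groups (A and B"), and "Instead the Group variable (A vs B) can be entered in the model using baseline mammography screening as a covariate". Its power table is labelled "Power for 357/arm (Groups A and B combined"), and the sample "will provide 80% power to detect differences between any pair of the four randomized arms for Aim 1". Hypothesis 1, as restated just before D.13, concerns CRC adherence and stage "when controlling for adherence to BC screening at baseline".

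Group is also a design stratum. D.12 states: "Enrollment will be stratified by women adherent to breast but not CRC screening and those adherent to neither in a 30%/70% ratio". Under D.1, random assignment to the "arms will be performed within both" Group A and Group B.

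D.13 (Analyses, Aim 1) has a different structure. Under "Group A (nonadherent to CRC but adherent to BC screening guidelines") it gives the 2x4 chi-square test of binary adherence, the logistic regression with three arm indicators, the contrasts among intervention arms and the binary stage-advancement analysis. Under the Group B heading it gives a three-level ordinal outcome (neither test, either test, both tests) and an ordinal analysis of stage. The covariate list in the Group A paragraph does not name baseline mammography group.

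**The concern.** D.13 is the section an analyst would program from, and it contains no pooled CRC efficacy analysis. Read literally, it tests the primary hypothesis in about 30% of the randomized women. For the other 70% it offers no arm comparison specific to CRC, because the middle ordinal category does not separate CRC from breast screening.

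The covariate that D.12 relies on is missing too. Within Group A, baseline breast-screening adherence is constant, so it cannot be controlled for there. In a pooled model the 0.20 imbalance screen is unlikely to bring Group in, because randomization within Group should keep it close to balanced across arms.

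Two things are at stake: the promise of 80% power for every pair of arms, and prespecification. With both versions in the plan, either population, with or without the Group term, could be defended after results are known. Aim 3 inherits the ambiguity because its interaction tests reuse the Aim 1 logistic models.

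**Working it through.** **Inputs, all from the D.12 table unless noted**
- Six-month CRC adherence: arm 1 usual care 20%, arm 2 web program 30%, arm 3 screening call 40%, arm 4 both 55%.
- Evaluable per arm: 357 combined, of which Group A 107 and Group B 250 (0.30 × 357 = 107.1). Enrolled per arm: 397, of which Group A 119.
- Alpha: not stated for Aim 1. Two-sided 0.05 without multiplicity adjustment is assumed and tested in step 1.
- Group A rates: not given. They are first taken equal to the combined rates, then varied.

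**Formula** (two proportions, n per arm, p̄ the mean of p₁ and p₂):

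power = Φ{ [ |p₁ − p₂| − 1.96·√(2p̄(1−p̄)/n) ] / √([p₁(1−p₁) + p₂(1−p₂)]/n) }

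**Step 1. Reproduce D.12 at n = 357**
- 1v2: (0.10 − 1.96 × 0.0324)/0.0322 = 1.13, power .871 (D.12: .87)
- 2v3: (0.10 − 1.96 × 0.0357)/0.0355 = 0.85, power .801 (D.12: .80)
- 3v4: (0.15 − 1.96 × 0.0374)/0.0370 = 2.08, power .981 (D.12: .98)
- The other three pairs exceed .99, as in D.12.

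Alpha 0.10 would give .93 and .88 for 1v2 and 2v3; alpha 0.01 would give .70 and .59. Of these levels only 0.05 fits the table.

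**Step 2. Same rates and alpha at n = 107, as D.13 is headed**
- 1v2: (0.10 − 1.96 × 0.0592)/0.0588 = −0.27, power .393
- 2v3: (0.10 − 1.96 × 0.0652)/0.0649 = −0.43, power .334
- 3v4: (0.15 − 1.96 × 0.0683)/0.0675 = 0.24, power .595

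| Contrast | n = 357 | n = 107 | n = 119 (no attrition) | n per arm for 80% |
|---|---|---|---|---|
| 1v2 | .871 | .393 | .429 | 294 |
| 2v3 | .801 | .334 | .365 | 356 |
| 3v4 | .981 | .595 | .641 | 173 |
| 1v3 | >.99 | .897 | .925 | 82 |
| 2v4 | >.99 | .964 | .978 | 61 |
| 1v4 | >.99 | >.99 | >.99 | 29 |

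Exact enumeration of the uncorrected chi-square test at 107 per arm gives .398, .339 and .587 for the first three rows, so the approximation is not driving the result.

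**Step 3. Overall 2x4 test at 107 per arm**

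The mean rate is 0.3625. Noncentrality = 107 × Σ(pᵢ − 0.3625)²/(0.3625 × 0.6375) = 31.0 on 3 df, power .999.

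**Step 4. Vary the Group A rates at 107 per arm**

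Either all four rates are shifted together by up to 10 points in each direction, or the odds ratios are held fixed while usual care runs from 10% to 30%. Over both sets: 1v2 .26 to .54, 2v3 .24 to .39, 3v4 .51 to .62. These three stay below .80 throughout. 1v3 runs from .72 to .96.

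**The case against.** The best defence is that D.12 already settles the matter. It replaces the separate-group design explicitly, gives its reasons and restates Hypothesis 1, so the Group A heading in D.13 is a leftover label. There is support for this reading. The Specific Aims put Hypothesis 1 under the same heading while controlling for a variable that is constant in Group A, and the D.13 paragraph mentions a covariate for mammography analyses, an outcome Group A does not have in Aim 1. The omnibus test keeps nearly full power, so only the follow-on contrasts suffer. The Aim 3 site comparison also models CRC adherence with arm terms and no Group A limit.

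Part of this stands. The intent of D.12 is clear, the omnibus test is safe, and the power loss occurs only if D.13 is followed. But the Group B text in D.13 refers back to Hypothesis 1 as the Group A analysis, so the restriction runs beyond one heading. D.12 promises 80% power for every pair of arms, and D.13 plans all six comparisons. The Aim 3 model tests site differences, not arm efficacy, and does not supply the missing analysis.

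One side issue is open to interpretation. D.13 lists screening history under the 0.20 screen and then says that two CRC-history covariates will be included. The second statement may only define how history is coded.

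**Conclusion.** The concern holds and should be fixed before analysis. D.12 and D.13 name different populations for the primary CRC analysis, and D.13 omits the Group term that D.12 requires. Followed as written, D.13 leaves contrasts 1v2, 2v3 and 3v4 at about .39, .33 and .59 against a stated 80%; the other three pairs and the overall test remain adequate.

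The count of three in six assumes two-sided alpha 0.05 without multiplicity adjustment and combined-sample rates in Group A. A Bonferroni correction over six pairs would bring 1v3 below 80% as well (.715), as would some of the alternative Group A rates in step 4. No rate scenario examined rescues the three failing pairs. The contradiction itself depends on none of these assumptions.

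**What to change.** Rewrite Hypothesis 1 under Aim 1 in D.13 and remove its Group A heading:
- One binary logistic model for CRC adherence in all randomized women (Groups A and B), with the arm terms and the planned contrasts.
- Group (baseline mammography adherence, the randomization stratum) as a fixed covariate, in the model regardless of the 0.20 screen.
- The initial 2x4 chi-square test and the CRC stage-advancement analysis in the same population.
- The ordinal model kept as the Group B secondary analysis, relabelled Hypothesis 2.
- A plain statement that the CRC screening-history covariates are always included, so that the two sentences on them agree.

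In the same edit, align the Group A heading over Hypothesis 1 in the Specific Aims, and the Aim 2 label, which means the Group B outcome in D.12 but cost-effectiveness elsewhere.

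The cost is wording only. Group and screening history are already collected, and no added visits, data or participants are needed.
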